6.1.13 Tumor Assessment

Tumor time point response assessment will be performed by the investigators according to RECIST Version 1.1 ([Appendix 8](#)) or RANO criteria for glioma subjects ([Appendix 9](#)). The tumor assessments will be performed during screening, every 8 weeks (± 1 week) beginning on C1D1 for the first 24 weeks, and every 12 weeks (± 2 weeks) thereafter as specified in [Table 1](#) and [Table 2](#), through EOT or end of Efficacy Follow-up (if applicable).

All measurable and evaluable lesions should be assessed and documented using image-based evaluation. All subjects are to be evaluated utilizing contrast-enhanced computed tomography (CT) scan or positron emission tomography (PET) scan or Gd MRI for glioma subjects to identify and follow selected lesions throughout the study. In addition, other radiographic or scintigraphic procedures (such as radionuclide bone scans), as deemed appropriate by the investigator, will be performed to assess sites of neoplastic involvement.

Tumor assessments completed as standard of care prior to signing of the informed consent but, within 28 days of first dose of study treatment, may be used as baseline scans. Assessments throughout the study should be made using the same modality as used at Screening.

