6.1.20 Follow-up Period

Safety Follow-up

Subjects who have completed the study treatment will be evaluated for safety 30 days (± 7) days following the EOT visit for study drug-related AEs until resolution and SAEs until resolution regardless of relationship to study treatment.

Efficacy Follow-up

Subjects who discontinue the study drug due to reasons other than disease progression, death, lost to follow-up, or withdrawal of consent will remain on study and will be followed every 12 weeks (± 14 days) from EOT visit for tumor assessment until disease progression, initiation of new anticancer therapy, withdrawal of consent, lost to follow-up, death, or the end of the study, whichever comes first.

Survival Follow-up

All subjects in expansion cohorts A, B, and D may be followed for survival status every 12 weeks (± 14 days), for a maximum of 2 years from EOT visit until death, lost to follow-up, or withdrawal of consent. Survival information can be obtained via phone, and information will be documented in the source documents and relevant eCRFs.

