In the derivation of duration of response, if a patient has a tumor assessment after two or more consecutive missed or inadequate tumor assessments, the patient will be censored at the last adequate tumor assessment. The following provides the rules for determining whether two or more consecutive tumor assessments are missed, of note, the relative day in the rules refers to the first dose date of study drug.

- If the tumor assessment date is prior to day 1 of week 17 (relative day $< (16 + 1) \times 7 + 1 = 120$), and the difference between the tumor assessment date and the next adjacent adequate tumor assessment ≥ 126 days ($= 2 \times (8 \text{ weeks} \times 7 + 7)$), then the tumor assessment is considered as occurring after two or more consecutive missing tumor assessments;

- If the tumor assessment date is between day 1 of week 17 and day 1 of week 25 (relative day between $(16 + 1) \times 7 + 1 = 120$ and $(24 + 1) \times 7 + 1 = 176$), and the difference between the tumor assessment date and the next adjacent adequate tumor assessment ≥ 161 days ($= (8 \text{ weeks} * 7 + 7 + 12 \text{ weeks} * 7 + 2 \text{ weeks} * 7)$), then the tumor assessment is considered as occurring after two or more consecutive missing tumor assessments;
- If the tumor assessment date is on or after day 1 of week 25 (relative day $\geq (24 + 1) \times 7 + 1 = 176$), and the difference between the tumor assessment date and the next adjacent adequate tumor assessment ≥ 196 days ($= 2 * (12 \text{ weeks} * 7 + 2 \text{ weeks} * 7)$), then the tumor assessment is considered as occurring after two or more consecutive missing tumor assessments.

Reasons for censoring are included in [Table 4](#) following the hierarchy.

Table 4 Duration of Response Censoring Reasons and Hierarchy

Hierarchy	Condition	Censoring Reason
1	New anti-tumor therapy started prior to PD	New anti-tumor therapy started prior to PD
2	Two or more consecutive missed or inadequate radiological assessment visits	Two or more consecutive missed or inadequate radiological assessment visits
3	Drops out before end of study, no PD or death, lost to follow-up	No death nor PD, lost to follow-up
4	Drops out before end of study no PD or death, withdrawal by subject from the study	No death nor PD, withdrawal by subject
5	No death nor PD by the time of data cut-off for the analysis	No death nor PD by the time of data cut-off for the analysis

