4.2.1.5. Progression-free Survival

PFS is defined as the time (months) from the date of first administration of study treatment until the first radiographic documentation of objective progression as assessed by investigator using RECIST v1.1 or RANO criteria for glioma patients, or death from any cause.

More specifically, PFS will be determined using all the assessment data up until the last evaluable

visit prior to or on the date of

- (i) disease progression as defined by RECIST Version 1.1 or RANO or death; or
- (ii) withdrawal of consent or lost to follow-up; or
- (iii) receiving subsequent anti-cancer medication, whichever is earlier.

Patients without report of PD or death from any cause at the time of analysis are censored as described in [Table 5](#) below.

The PFS time will always be derived based on scan dates not tumor assessment dates. RECIST or RANO assessments/scans contributing towards a particular visit may be performed on different dates. The following rules are applied:

- Date of progression is determined based on the earliest of the dates of the component that triggered the progression.
- When censoring a patient for PFS, the patient is censored at the latest of the dates contributing to a particular overall visit assessment.

Table 5 Outcome and Event or Censoring Dates for PFS

Rule	Situation	Date of Progression or Censoring	Outcome
1	PD documented from radiological assessment visits	Date of first documented disease progression	Event
2	Death without PD or death after one missing radiological assessment visit	Date of death	Event
3	No baseline nor post-baseline radiological assessments available	Date of first administration of study treatment	Censored
4	No death or PD by the time of data cut-off for analysis	Date of last adequate radiological assessment	Censored
5	Early discontinuation (lost to follow-up or withdrawal of consent) of study without death or PD	Date of last adequate radiological assessment	Censored
6	New anti-tumor therapy started prior to PD	Date of last adequate radiological assessment prior to or on date of initiation of new therapy visit	Censored
7	Death or PD after two or more consecutive missed or inadequate radiological assessment visits	Date of last adequate radiological assessment prior to missed visits	Censored

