Note: An adequate radiologic assessment is defined as an assessment where the Investigator determined radiological response is CR, PR, SD, or PD. If PD and new anti-cancer medication occur on the same day, will assume that the progression was documented first, e.g. outcome is progression and the date is the date of the assessment of progression

Note: The same algorithm for determination of two or more consecutive missing or inadequate assessments can be found in [Section 4.2.1.3](#).

PFS is calculated as (date of progression or censoring as per rules in [Table 5](#) – date of first administration of study treatment + 1)/30.4375. Reasons for censoring are included in [Table 6](#) following the hierarchy.

Table 6 PFS Censoring Reasons and Hierarchy

Hierarchy	Condition	Censoring Reason
1	No baseline nor post-baseline tumor assessments available	No baseline nor post-baseline tumor assessments
2	New anti-tumor therapy started prior to PD	New anti-tumor therapy started prior to PD
4	Two or more consecutive missed or inadequate radiological assessment visits	Two or more consecutive missed or inadequate radiological assessment visits
5	Drops out before end of study, no progression or death, lost to follow-up	No death nor PD, lost to follow-up
6	Drops out before end of study no progression or death, withdrawal by subject from the study	No death nor PD, withdrawal by subject
7	No death nor PD by the time of data cut-off for the analysis	No death nor PD by the time of data cut-off for the analysis

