5.2.9. Efficacy Analyses

The safety analysis set will be used for PFS, and the response evaluable analysis set will be used for anti-tumor responses such as BOR, DoR, DCR, and TTR. No formal hypothesis testing is planned for this study. Two-sided 95% confidence intervals (CIs) will be calculated in the applicable summary, unless otherwise specified.

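### The SAP's missed-scan rule ignores the post-treatment scan schedule, so progression found after one missed follow-up scan can be censored as if two had been missed

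*SAP*

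**What the plan says.** Two scan clocks are in force. On treatment, Protocol 6.1.13 sets scans every 8 weeks (±1 week) from C1D1 to week 24 and every 12 weeks (±2 weeks) after that. For patients who stop the drug without progression, Protocol 6.1.20 and SAP 2.2 set scans every 12 weeks (±14 days) "from EOT visit for tumor assessment until disease progression, initiation of new anticancer therapy". Protocol 6.1.13 blurs this by running its own schedule "through EOT or end of Efficacy Follow-up (if applicable").

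In SAP Table 5, rule 7 censors "Death or PD after two or more consecutive missed or inadequate radiological assessment visits" at the last adequate scan before the gap. Rule 2 counts "Death without PD or death after one missing radiological assessment visit" as an event. Table 3 does the same for DoR.

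SAP 4.2.1.3 puts rule 7 into practice by comparing "the difference between the tumor assessment date and the next adjacent adequate tumor assessment" with 126, 161 or 196 days. The threshold depends on a bracket with cut-offs at days 120 and 176, and "the relative day in the rules refers to the first dose date of study drug". For PFS, the note to Table 5 says: "The same algorithm for determination of two or more consecutive missing or inadequate assessments can be found in" Section 4.2.1.3. No part of the rule refers to the EOT visit.

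**The concern.** The thresholds are meant to detect two missed visits, but they were built from the schedule that applies while the patient takes the drug. Once the patient is past EOT, scans are 12 weeks apart and start from a new date. A gap that means two missed scans on treatment can then mean one missed scan, or in a narrow case none. A progression that rule 1 makes an event is then moved back to the last on-treatment scan as a censored time. Whether that happens depends on why and when the drug was stopped, which is unlikely to be unrelated to prognosis. The results are broken down by dose level and disease type, so one reclassified event can move a median.

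**Working it through.** **Inputs.** Intervals and windows come from Protocol 6.1.13 and 6.1.20, and thresholds and cut-offs from SAP 4.2.1.3. C1D1 is day 1, so scans at weeks 8, 16, 24 and 36 fall nominally on days 57, 113, 169 and 253.

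**1. The SAP's own figures.** 2 × (56 + 7) = 126. (56 + 7) + (84 + 14) = 161. 2 × (84 + 14) = 196. (16 + 1) × 7 + 1 = 120. (24 + 1) × 7 + 1 = 176. All five reproduce, and every interval in them is an on-treatment interval.

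**2. Gaps after drug stop.** Let x be the EOT visit day minus the day of the last adequate scan.
- No scan missed: gap = x + 84 (±14).
- One scan missed: gap = x + 168 (±14).

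To ensure that no on-treatment scan was missed, EOT is kept before the next scan window opens (days 106, 162, 239, 323). So x is at most 48 after weeks 8 and 16, and at most 69 after weeks 24 and 36.

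**3. Which scan sets the bracket.** The SAP wording allows either. Its conclusion describes the indexed scan as the one that follows the misses, which suggests the later scan. But it measures to the next scan, and 161 is one 8-week plus one 12-week interval. That is what lies ahead of a week-16 scan (weeks 24 and 36). Looking back from a scan in weeks 17 to 25, both preceding intervals are 8 weeks. The formula therefore supports the earlier scan. Both readings are shown.

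**4. One follow-up scan missed, then PD.**

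| Last scan | Threshold (earlier scan sets bracket) | Censored when |
|---|---|---|
| Week 8 (day 57) | 126 | any x, even 14 days early (154 ≥ 126) |
| Week 16 (day 113) | 126 | any x, likewise |
| Week 24 (day 169) | 161 | any x if on time (168 ≥ 161); only x ≥ 7 if 14 days early (x + 154) |
| Week 36 or later | 196 | x ≥ 28 if on time (x ≥ 42 if 14 days early, x ≥ 14 if 14 days late) |

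If the later scan sets the bracket, the second follow-up scan falls on day 57 + 168 = 225 at the earliest with on-time scans. The threshold is then 196 throughout, and PD is censored from x ≥ 28.

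**5. No scan missed.** On the earlier-scan reading with a day-57 scan, x + 84 ≥ 126 requires x ≥ 42, so EOT on days 99 to 105. If the follow-up scan is 14 days late but in window, x + 98 ≥ 126 requires x ≥ 28, so EOT on days 85 to 105. On the later-scan reading there is no such case after nominal week-8 to week-36 scans.

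**6. Example.** Last scan day 57, EOT day 105 (x = 48). Months are study day / 30.4375.
- PD at the first follow-up scan, day 189: gap 132. Earlier-scan reading: censored at day 57 (1.87 months) instead of an event at 6.21 months. Later-scan reading: event.
- First scan missed, PD at the second, day 273: gap 216. Censored at 1.87 months on both readings (216 ≥ 126 and 216 ≥ 196), instead of an event at 8.97 months.
- Two scans missed, PD at the third, day 357: gap 300. Correctly censored.

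On the EOT clock, two scans are missed only if the next one falls after EOT + 2 × 84 + 14 = EOT + 182, here day 287 (gap 230).

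**7. Cut-offs at days 113 and 169.** The SAP labels days 120 and 176 as day 1 of weeks 17 and 25, but by the calendar those are days 113 and 169. With those values, on the earlier-scan reading, a nominal week-16 scan carries 161 and a week-24 scan 196. The no-miss cases that exist after those scans under 120/176 (EOT days 155 to 161 on time; 141 to 161 and 232 to 238 if late in window) disappear. One-miss censoring remains: any x after week 16 on time (168 ≥ 161), and x ≥ 28 after week 24. The week-8 results do not change.

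**The case against.** Several parts of the opposing case stand.

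- **Ambiguous index scan.** If the later scan sets the bracket, the no-miss case goes and one-miss censoring needs x ≥ 28.
- **A scan at EOT.** Protocol 6.1.19 describes safety assessments at EOT, but the imaging row of Table 1 cannot be read reliably here. If a scan is done at EOT, x = 0. The longest no-miss gap is 84 + 14 = 98, so that case vanishes. A one-miss gap of 168 then exceeds only the 126 and 161 thresholds, and on the later-scan reading it is never censored (168 < 196).
- **One clock throughout.** If Protocol 6.1.13 means that the C1D1 schedule continues in follow-up, the mismatch goes. Protocol 6.1.20 and SAP 2.2, however, both state the EOT anchor.
- **Stakes.** "No formal hypothesis testing is planned for this study", and PFS and DoR are secondary. Only patients who stop without progression and start no new therapy before PD are exposed, since rule 6 censors the others.

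A reader might also infer that PFS and DoR are biased upward. The documents do not support that. Censoring back also removes event-free time at risk. With ten assumed events on days 40, 57, 57, 60, 112, 113, 113, 169, 184 and 253, censoring the day-184 event at day 57 lowers the Kaplan-Meier estimate at day 112 from 0.50 to 0.467 and at day 169 from 0.20 to 0.117. After day 184 it is higher (0.117 against 0.10).

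Nor can it be said that deaths after one missed visit are censored against rule 2. The gap rule compares two scan dates and gives no formula for a death date, so for deaths the rule is undefined.

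**Conclusion.** The rule is wrong as written for patients past EOT. Unless an EOT scan is routine, it can class one missed follow-up scan as two and censor a documented progression on either reading of the index scan, contrary to rule 7.

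A reader might infer that patients who miss nothing generally lose their events. That goes too far: it needs the earlier-scan reading and an EOT visit late in the scan interval. If EOT days were spread evenly between scans (an assumption), it would affect 7/49 = 14% of such patients whose last scan was at week 8, with a range from 0% to 21/49 = 43% over the ±14-day window. It would also be wrong to call the problem wholly separate from the day-120/176 cut-offs, since the week-16 and week-24 no-miss cases depend on them. The one-miss problem does not.

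The number affected cannot be derived, because the documents do not say how many patients stop without progression. Part 1 is estimated at 27 to 36 patients. The conclusion assumes nominal on-treatment scan days and the EOT-anchored follow-up. The SAP cites Protocol Amendment 3 while the protocol supplied is Amendment 2, but the SAP's own text carries that follow-up schedule. The correction is worth making before database lock.

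**What to change.** In SAP 4.2.1.3, and by reference 4.2.1.5:

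1. State which scan sets the bracket.
2. For patients past the EOT visit, count missed visits against the follow-up schedule: EOT + 12 weeks ±14 days, then every 12 weeks. Censor only when two consecutive scheduled scans were actually missed, counting the last due on-treatment scan if it was missed.
3. Apply the same count to deaths, so that rules 2 and 7 can both be programmed.

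Reconcile Protocol 6.1.13 with 6.1.20 so that one scan clock applies after drug stop.

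The cost is a short SAP clause and a small programming change that uses the EOT date already collected. PFS and DoR estimates may change slightly, in a direction that cannot be known in advance.

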1.3 Schedule of Events

The schedule of events (SOE) is presented in [Table 1](#) and [Table 2](#).

Table 1 Schedule of Events (excluding Cohort C-1)

Cycle/Period	Pre- screening	Screening	C1				C2		C3+	EOT	Safety Follow- up	Efficacy Follow- up	Survival Follow- up
Visit			D1	D8	D15	D22	D1	D15	D1	Within 7 Days After the Last Dose	30 Days After the EOT Visit	Every 12 Weeks From EOT Visit	Every 12 Weeks From EOT Visit
Visit Window (days)	--	-28 to -1	--	±1	±1	±1	±1	±1	±3	±3	±7	±14	±14
Activities													
Pre-screening informed consent ¹	X												
Main informed consent ²		X											
IDH mutational status ³	X	X								X			
Medical history and demographics ⁴	X	X											
Prior and concomitant medications and concomitant procedures ⁵		X	X	X	X	X	X	X	X	X	X	X	
Height		X											
Physical examination, vital signs, and weight ⁶		X	X	X	X	X	X	X	X	X			
ECOG performance status ⁶		X	X		X		X	X	X	X			
Ophthalmologic examination ⁷		X						X (±1 week)	Every 12 weeks (±1 week) from C4D1				
Laboratory evaluations ⁶													
Hematology ⁸		X ⁹		X	X	X	X	X	X	X	X		
Blood chemistry ¹⁰		X ⁹		X	X	X	X	X	X	X	X		
Blood amylase and lipase		X ⁹		X	X	X	X	X	X	X			
Fasting lipid panel ¹¹		X ⁹			X		X		X	X			
Coagulation indicators ¹²		X ⁹			X		X		X				
Pregnancy test ¹³		X	X				X		X	X	X		
Urinalysis ¹⁴		X ⁹					X		X	X			

Table 1 Schedule of Events (excluding Cohort C-1)

Cycle/Period	Pre-screening	Screening	C1				C2		C3+	EOT	Safety Follow-up	Efficacy Follow-up	Survival Follow-up
Visit			D1	D8	D15	D22	D1	D15	D1	Within 7 Days After the Last Dose	30 Days After the EOT Visit	Every 12 Weeks From EOT Visit	Every 12 Weeks From EOT Visit
Visit Window (days)	--	-28 to -1	--	±1	±1	±1	±1	±1	±3	±3	±7	±14	±14
Activities													
Virological screening ¹⁵		X											
HbA1C		X ⁹			X		X		X	X			
PK and PD assessments	Refer to Appendix 1												
12-lead ECG ^{6,16}	Refer to Appendix 1												
ECHO/MUGA scan		X					X		C3D1 then Day 1 of every odd cycle (ie, C5D1, C7D1, etc.) (±1 week)				
Tumor evaluation/imaging ¹⁷		X	Every 8 weeks from C1D1 during the first 24 (±1) weeks and every 12 (±2) weeks thereafter								X		
Tumor tissue for exploratory biomarker evaluation. Applies to Cohorts A, B, and D only ¹⁸		X					X±7 days		At disease progression only in dose expansion				
Blood for gene mutation analysis ¹⁹		X	Only in dose expansion; refer to Appendix 1										

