4. ENDPOINTS

4.1. General Principles for Derived and Transformed Data

4.1.1. Reference Start Date and End Date and Study Day

Reference start date is defined as the first date when a non-zero dose of study drug was administrated (first administration/dose date). Day 1 is the day of the first dose of study treatment in Cycle 1.

Study day will be calculated from the reference start date, and it will be used to show start/stop day of assessments and events relative to the first administration of study treatment.

- If the date of the event is on or after the reference start date, Study day = (date of event – reference start date) + 1.
- If the date of the event is prior to the reference start date, Study day = (date of event – reference start date).

In the situation where the event date is partial or missing, the date will appear partial or missing in the listings.

Reference end date is defined as the last date when a non-zero dose of study drug was administered.

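### The SAP's test for two missed scans in a row switches thresholds at the end of the week-16 and week-24 windows, so on its most natural reading a progression after one missed scan there is censored in PFS and DoR

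*SAP*

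**What the plan says.** Protocol 6.1.13 schedules scans every 8 weeks "beginning on C1D1 for the first 24 weeks, and every 12 weeks" after that. The windows in Protocol 1.3 (Table 1) are "during the first 24 (±1) weeks and every 12 (±2) weeks thereafter".

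In the SAP, rule 7 of Table 5 censors PFS for "Death or PD after two or more consecutive missed or inadequate radiological assessment visits", at the last adequate scan before the gap. Rule 7 of Table 3 does the same for DoR. Rule 1 of each table counts a documented progression as an event, and rule 2 keeps a death after one missing visit as an event.

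SAP 4.2.1.3 makes the missed-scan condition operational, and SAP 4.2.1.5 applies the same algorithm to PFS. It tests the "difference between the tumor assessment date and the next adjacent adequate tumor assessment" against one of three thresholds:

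- "If the tumor assessment date is prior to day 1 of week 17" (relative day below 120): 126 days.
- "If the tumor assessment date is between day 1 of week 17 and day 1 of week 25" (days 120 to 176): 161 days.
- From day 176 onward: 196 days.

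Relative day is counted from first dose, and SAP 4.1.1 says "Day 1 is the day of the first dose of study treatment in Cycle 1".

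**The concern.** Each threshold is the longest gap that in-window scans can leave when one visit is missed, so the right one depends on which two intervals follow the scan. The intervals change from 8 to 12 weeks at week 24. A week-16 scan is followed by 8 and then 12 weeks, and a week-24 scan by 12 and 12. The boundaries should therefore separate week 8 from week 16, and week 16 from week 24. Days 120 and 176 instead fall at the far end of the week-16 and week-24 windows, so nearly every on-time scan at those visits gets a threshold one step too short.

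A patient who missed one scan and then had documented progression would be treated as having missed two. Rules 1 and 7 together call for an event there; the algorithm gives a censoring at the earlier scan. The rule will be programmed as written, and efficacy is shown by dose level and disease type in a part expected to enroll about 27 to 36 subjects, so a single lost event can be visible in a Kaplan-Meier estimate.

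**Working it through.** **1. The SAP's own figures.** (16+1)×7+1 = 120; (24+1)×7+1 = 176; 2×(56+7) = 126; (56+7)+(84+14) = 161; 2×(84+14) = 196. All reproduce as arithmetic.

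**2. The labels.** With Day 1 as first dose, day 1 of week 17 is 16×7+1 = 113 and day 1 of week 25 is 24×7+1 = 169. Days 120 and 176 are day 1 of weeks 18 and 26. Day 176 also falls in both the second and third brackets; it is put in the third below.

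**3. Calendar.** Nominal day = 7×week+1, with ±7 days to week 24 and ±14 days after.

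| Scan | Nominal day | Window | Next two intervals | Threshold needed | Threshold applied (scan before the gap sets bracket) |
|---|---|---|---|---|---|
| Week 8 | 57 | 50–64 | 8+8 weeks | 126 | 126 |
| Week 16 | 113 | 106–120 | 8+12 weeks | 161 | 126 on days 106–119 |
| Week 24 | 169 | 162–176 | 12+12 weeks | 196 | 161 on days 162–175 |
| Week 36 | 253 | 239–267 | 12+12 weeks | 196 | 196 |
| Week 48 | 337 | 323–351 | 12+12 weeks | 196 | 196 |

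**4. Two on-time examples, one scan missed in each.** PFS in months is study day/30.4375.

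- Scan at week 16, week 24 missed, progression at week 36: gap 253−113 = 140 ≥ 126, flagged. Censored at 113/30.4375 = 3.7 months instead of an event at 253/30.4375 = 8.3.
- Scan at week 24, week 36 missed, progression at week 48: gap 337−169 = 168 ≥ 161, flagged. Censored at 169/30.4375 = 5.6 months instead of an event at 337/30.4375 = 11.1.

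**5. All in-window day pairs.** Each sequence has 15×29 = 435 pairs.

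- Week 16 to week 36: days 106–113 are flagged for all 29 later days (8×29 = 232). Days 114–119 give 28+27+26+25+24+23 = 153. Day 120 gives none. Total 385/435 (89%).
- Week 24 to week 48: days 162–175 give 29 down to 16, which sum to 315. Day 176 gives none. Total 315/435 (72%).

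| Boundaries | Week 16→36, one missed | Week 24→48, one missed | Two missed |
|---|---|---|---|
| 120/176 (SAP) | 385/435 | 315/435 | all flagged |
| 113/169 (labels corrected) | 203/435 | 182/435 | all flagged |
| 106/162 (window openings) | 1/435 | 0/435 | all flagged |

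Correcting only the labels is therefore not enough.

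**6. Where the rule already works.** One scan missed after week 8 has a nominal gap of 169−57 = 112 < 126 (1/225 pairs flagged, an exact tie). One missed after week 36 has 421−253 = 168 < 196 (1/841, again a tie).

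**7. Direction of the effect.** Censoring the first patient at 3.7 months removes an event at 8.3, so later estimates lose a downward step. It also shrinks the risk set in between. Another patient's event there, with n at risk, multiplies the curve by 1−1/(n−1) instead of 1−1/n, which is lower. A 6-month estimate can therefore fall while later ones rise.

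**8. The other reading.** If the later scan sets the bracket, both single-miss sequences in step 5 give 0/435. But week 8 to week 36, with weeks 16 and 24 both missed, is tested against 196 and flagged in only 225/435 pairs (52%).

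**The case against.** The strongest reply is that each bullet of the rule ends by describing the tumor assessment as the one that comes after the missed visits. Taken literally, that is the later scan, and then neither single-miss sequence is flagged. The ambiguity is real, but this reading does not rescue the rule. All intervals up to week 24 are 8 weeks, so an 8+12-week threshold for a later scan on days 120 to 176 has no rationale. The first two brackets could never be triggered between post-baseline scans: the longest gap from the earliest week-8 day is 176−50 = 126 days, short of 161, and in the first bracket 119−50 = 69, short of 126. The phrase about the next adjacent assessment also points forward. And this reading misses about half of the true two-missed week 8 to week 36 gaps. Both readings misclassify.

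The reply on importance largely stands. PFS and DoR are secondary, no hypothesis is tested, and the MTD/RP2D and safety results are untouched. DoR is affected only among responders. Swimmer plots and tumor listings would still show the affected patient's course. This limits the severity; it does not make the rule right.

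**Conclusion.** The boundaries are misplaced and should be corrected; severity is moderate. With the scan before the gap setting the bracket, a documented progression after exactly one missed scan is turned into a censoring when the last adequate scan was the week-16 scan (days 106–119) or the week-24 scan (days 162–175), in 89% and 72% of in-window day pairs.

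A reader might infer more than the documents support:

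- That any single missed scan leads to censoring. It does not: after week 8, or from week 36 onward, the rule works apart from exact ties.
- That 89% and 72% are shares of patients. They are shares of day pairs; the documents give no missed-scan rate.
- That deaths are lost in the same way. The test compares two scans, and rule 2 keeps a death after one missing visit. How the gap test reaches deaths is simply not stated.
- That PFS and DoR are biased upward throughout. Events are lost and later estimates tend to rise, but the sign at a given landmark can vary.

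The result assumes the calendar in protocol Amendment 2. The SAP cites Amendment 3, which is not among the documents, but the SAP's own week 16, week 24, 8-week and 12-week figures agree with that calendar.

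**What to change.** State in SAP 4.2.1.3 that the bracket is set by the last adequate assessment before the gap, and set the boundaries at the window openings, (16−1)×7+1 = 106 and (24−1)×7+1 = 162:

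- relative day below 106: 126 days;
- days 106 to 161: 161 days;
- day 162 or later: 196 days.

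Apply the same text to PFS, and drop the week labels or make them agree with the day numbers. Replacing ≥ by > in the gap test would also remove the remaining exact ties, and all two-missed sequences would still be flagged.

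Two matters need their own sentence, because new boundaries do not settle them. One is how the rule applies when the event is a death. The other is scans after end of treatment, which run every 12 weeks from the EOT visit and not on the week 8/16/24 calendar. For example, with a last scan on day 57, EOT on day 70, the follow-up scan due on day 154 missed and the next on day 238, the gap is 181 days. That exceeds 126, so even the corrected rule would flag one missed scan as two.

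The cost is a few lines of SAP text and one programming change before database lock. No new data are needed.
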